8.3.1.3. Safety

The primary analysis set for safety analyses is defined as the Safety Analysis Set, which will include all randomized participants who have received at least one dose of study drug.

All data collected during study will be included in the safety summaries.

8.3.1.4. Pharmacokinetics

8.3.1.4.1. Pharmacokinetic (PK) Substudy Analysis Set

The PK Substudy Analysis Set, which will include all randomized participants who are enrolled into the Optional PK Substudy, have received at least 1 dose of study drug, and have at least 1 nonmissing concentration value reported by the PK laboratory for corresponding analytes (eg, LEN or metabolites, if applicable).

8.3.1.4.2. Pharmacokinetic (PK) Analysis Set

The PK Analysis Set, which will include all randomized participants who have received at least 1 dose of study drug, and have at least 1 nonmissing concentration value reported by the PK

laboratory for the corresponding analytes (eg, GS-5423, GS-2872, LEN and metabolites, if applicable).

8.3.1.5. Immunogenicity

The Immunogenicity Analysis Set will include all randomized participants who have received at least 1 dose of study drug and have had at least 1 nonmissing value for each immunogenicity evaluation (eg, anti-GS-5423 or anti-GS-2872).

8.3.2. Data Handling Conventions

Natural logarithm transformation for key PK parameters, such as AUC and C_{\max} will be applied for PK analysis, as appropriate.

For summary statistics, PK concentration values below the limit of quantitation (BLQ) will be treated as zero at predose and one-half the lower limit of quantitation (LLOQ) for postdose time points.

Laboratory data that are continuous in nature but are less than the LLOQ or above the upper limit of quantitation (ULQ) will be imputed to the value of the lower or upper limit minus or plus 1 significant digit, respectively (eg, if the result of a continuous laboratory test is < 20 , a value of 19 will be assigned).

Missing data can have an impact upon the interpretation of the study data. In general, values for missing data will not be imputed. However, a missing pretreatment laboratory result would be treated as normal (ie, no toxicity grade) for the laboratory abnormality summary.

8.4. Demographic and Baseline Characteristics Analysis

Demographic and baseline measurements will be summarized using standard descriptive methods by treatment group.

Demographic summaries will include sex, race/ethnicity, and age. Baseline data will include a summary of body weight, height, body mass index, and HIV-1 infection.

8.5. Efficacy Analysis

The proportion of participants with HIV-1 RNA < 50 copies/mL at Weeks 26 as defined by the FDA-defined snapshot algorithm will be summarized by treatment group and overall using the Full Analysis Set. The 95% CIs will be constructed on the exact method. These efficacy endpoints will be compared between treatment groups by Fisher exact test.

The proportion of participants with HIV-1 RNA ≥ 50 copies/mL at Weeks 26 as defined by the FDA-defined snapshot algorithm will also be summarized by treatment group and overall in a similar manner.

The change from baseline in CD4+ cell count at Weeks 26 will be summarized by treatment group using descriptive statistics. Treatment-emergent resistance to study drugs will be summarized by treatment group.

8.6. Safety Analysis

All safety data collected on or after the date that study drug was first dispensed up to the end of the protocol-defined follow-up period will be summarized by treatment group using Safety Analysis Set. Data for the pretreatment will be included in data listings. For participants who discontinue from only the oral LEN, only data collected up to 60 days after the last dose of the oral tablet will be included in the data summary.

8.6.1. Extent of Exposure

A participant's extent of exposure to study drug data will be generated from the study drug administration data. Exposure data will be listed.

8.6.2. Adverse Events

Clinical and laboratory AEs will be coded using the Medical Dictionary for Regulatory Activities (MedDRA). System organ class (SOC), high-level group term (HLGT), high-level term (HLT), preferred term, and lower-level term (LLT) will be attached to the clinical database.

Events will be summarized on the basis of the date of onset for the event. Any treatment-emergent AEs will be defined as any AE that begins on or after the date of first dose of study drug up to the end of the protocol-defined follow-up period. For participants who discontinue from only the oral LEN, only AEs collected up to 60 days after the last dose date will be considered treatment-emergent.

Summaries (number and percentage of participants) of treatment-emergent AEs (by SOC and preferred term) by treatment group will be provided. Additional summaries will include summaries for AEs by grade, investigator's assessment of relationship to study drug, and effect on study drug dosing.

8.6.3. Laboratory Evaluations

Selected laboratory data will be summarized using only observed data. Data and change from baseline at all scheduled time points will be summarized by treatment group.

Graded laboratory abnormalities will be defined using the grading scheme in the DAIDS toxicity grading scale, Version 2.1 ([Appendix 4](#)).

Incidence of treatment-emergent laboratory abnormalities, defined as values that increase at least one toxicity grade from baseline at any time postbaseline through the duration of the study, will be summarized by treatment group. If baseline data are missing, then any graded abnormality (ie, at least a Grade 1) will be considered treatment-emergent.

Laboratory abnormalities that occur before the first dose of study drug will be included in a data listing.

8.6.4. Other Safety Evaluations

Vital signs and ECG data will be summarized by treatment group.

8.7. Adjustments for Multiplicity

No adjustments are planned.

8.8. Pharmacokinetic Analysis

Serum or plasma concentrations of each analyte (eg, GS-5423, GS-2872, and LEN [and metabolites, if applicable]) will be summarized by nominal sampling time and treatment using descriptive statistics for PK Substudy Analysis Set or PK Analysis Set as appropriate. Pharmacokinetic parameters (AUC_{0-t} , AUC_{last} , $t_{1/2}$, C_{max} , T_{max} , T_{last} , C_t , as appropriate) will be listed and summarized using descriptive statistics (eg, sample size, arithmetic mean, geometric mean, coefficient of variation %, SD, median, Q1, Q3, minimum, and maximum) by treatment group or overall, as appropriate. Serum or plasma concentrations of each analyte over time will be plotted in semi-logarithmic and linear formats as mean \pm SD, and median (Q1, Q3), respectively.

8.9. Immunogenicity Analysis

Immunogenicity to GS-5423 and GS-2872 will be evaluated based upon the incidence of anti-GS-5423 antibody and anti-GS-2872 antibody formation, respectively. The number and percentage of participants positive or negative for anti-GS-5423 antibody and anti-GS-2872 antibody at each specified time point will be summarized, and supporting data including treatment, nominal visits, actual date and time of sampling, and anti-GS-5423 antibody and anti-GS-2872 antibody results will be included in a listing.

8.10. Sample Size

Although the sample size in this study is determined based on practical considerations and past experience with similar types of studies, assuming the 2 treatment groups have a similar virologic suppression rate, a total of 20 participants in the Primary Cohort will provide at least 35% power to show the lower bound of 95% CI for Week 26 virologic response rate (HIV-1 RNA < 50 copies/mL as defined by the FDA-defined snapshot algorithm) is greater than 83%. It was assumed that the virologic response rate at Week 26 was 95% (based on Gilead studies GS-US-380-1844 and GS-US-380-4030), 12% was a clinically tolerable margin for Phase 1b studies, and a one-sided exact test with a significance level 0.025 was used. The sample size and power calculations were made using the statistical software package PASS (Version 14, NCSS, LLC; Kaysville, Utah, USA).

The estimated 95% CI for possible range of VF rate is provided in [Table 8-1](#). For example, with 1 VF event occurrence (5% estimated VF rate), a sample size of 20 participants can provide 95% confidence that the true VF rate is unlikely to be higher than 24.9%.

Table 8-1. Estimated Virologic Failure Rate and its 95% CIs (from the Clopper-Pearson Exact CI) Based on Number of Virologic Failure Event in Each Group or in Total

Sample Size	20				
Number of VF Events	0	1	2	3	4
Estimate of Incidence of VF (%)	0.0	5.0	10.0	15.0	20.0
Lower Bound of 95% CI (%)	0.0	0.1	1.2	3.2	5.7
Upper Bound of 95% CI (%)	16.8	24.9	31.7	37.9	43.7

VF = virologic failure

Software: SAS® Version 9.4. (SAS Institute Inc., Cary, NC, USA)

A total of approximately 20 participants in the Primary Cohort will provide reasonable assessment of safety and the descriptive PK profile throughout the study. A total of up to 20 participants in the optional Pilot Cohort is based on practical considerations.

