4. PARTICIPANT POPULATION

4.1. Number of Participants and Participant Selection

Approximately 20 participants who meet all the eligibility criteria will be enrolled in the Primary Cohort. After GDRC review (Section 5.1.3), an optional Pilot Cohort of up to 20 additional participants may be added.

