5. INVESTIGATIONAL MEDICINAL PRODUCTS

5.1. Randomization, Blinding and Treatment Codes Access

5.1.1. Randomization

Participants will be assigned a screening number in the IRT system at the time of consent.

Once eligibility has been confirmed, the investigator or designee will randomize the participant using the IRT system. Once a participant number has been assigned to a participant, it will not be reassigned to any other participant. The participant number assignment and randomization must be performed in clinic at the Day 1 visit provided that all screening procedures have been completed and participant eligibility has been confirmed.

Participants in the Primary Cohort who meet all eligibility criteria will be randomized in a 1:1 ratio to Treatment Group 1 or Treatment Group 2. Participants in the Pilot Cohort who meet all eligibility criteria will be randomized in a 1:1 ratio to Treatment Group 1 or Treatment Group 2.

There is no stratification for randomization for the Primary Cohort.

For the optional Pilot Cohort, randomization will be stratified by the antibody (GS-5423 or GS-2972) to which the participant is sensitive.

The IRT will assign a study drug bottle or vials at the Day 1 visit for each participant.

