3.2.2. Grouping for Efficacy Analyses

For efficacy analyses, participants will be grouped as follows for table summary:

- **Primary Cohort**
 - Treatment Group 1: SC LEN + GS-5423 + GS-2872 10 mg/kg
 - Treatment Group 2: SC LEN + GS-5423 + GS-2872 30 mg/kg
 - Total Primary Cohorts: All participants from Treatment Groups 1 and 2 (for all tables and figure summary unless specified otherwise)
- **Pilot Cohort**
 - Treatment Group 1: SC LEN + GS-5423 + GS-2872 10 mg/kg
 - Treatment Group 2: SC LEN + GS-5423 + GS-2872 30 mg/kg
 - Total Pilot Cohorts: All participants from Treatment Groups 1 and 2 (for all tables and figure summary unless specified otherwise)

No pooled analyses will be conducted on the efficacy.

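### The virologic failure precision table is captioned as applying to each treatment group, but it is computed for n = 20, the cohort total; each group has about 10

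*Protocol*

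**What the plan says.** Protocol section 8.10 and SAP section 1.3 each contain a table of estimated virologic failure rates with exact 95% limits for 0 to 4 events. The caption in both is "Based on Number of Virologic Failure Event in Each Group or in Total". The only sample size shown is 20, and the worked example under section 8.10 also uses 20.

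The Primary Cohort is that size in total. Protocol section 4.1 states: "Approximately 20 participants who meet all the eligibility criteria will be enrolled in the Primary Cohort". Under Protocol section 5.1.1, participants in each cohort "will be randomized in a 1:1 ratio to Treatment Group 1 or Treatment Group 2". The optional Pilot Cohort has at most 20 and is split the same way. SAP section 3.2.2 reports efficacy by treatment group within each cohort and adds: "No pooled analyses will be conducted on the efficacy".

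The same sample size sections say that "a total of 20 participants in the Primary Cohort will provide at least 35% power" to show a lower 95% confidence limit above 83% for Week 26 response. The assumed true rate is 95%, and "a one-sided exact test with a significance level 0.025 was used".

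**The concern.** The caption claims for a single dose group a precision that only the two groups together have. The trial compares two doses of GS-2872, and Protocol section 8.5 reports efficacy by treatment group with exact intervals, so per-group precision is something a reader of the sample size section will look for.

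The printed rows mislead at group level in two ways. The limits are too narrow, and the point estimates are halved: one failure in a group of 10 is 10%, whereas the table shows 5%. Someone planning from the table would conclude that a dose group with no failures rules out failure rates above about 17%. With 10 participants it rules out only rates above about 31%.

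**Working it through.** **Inputs.** Table sample size 20 (Protocol 8.10, SAP 1.3). Primary Cohort about 20 in total (Protocol 4.1). Allocation 1:1 (Protocol 5.1.1), so 20 / 2 = 10 per group. No pooling of cohorts for efficacy (SAP 3.2.2).

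**Formula.** For x events in n, the Clopper-Pearson limits are the 2.5% quantile of Beta(x, n − x + 1) and the 97.5% quantile of Beta(x + 1, n − x). For x = 0 the lower limit is 0 and the upper limit is 1 − 0.025^(1/n).

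**Step 1: reproduce the printed table.** At n = 20 and x = 0, the upper limit is 1 − 0.025^(1/20) = 1 − 0.8316 = 16.8%, as printed. The other four columns also reproduce.

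**Step 2: repeat for a group of 10.** At x = 0, the upper limit is 1 − 0.025^(1/10) = 30.8%.

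| Events | As printed (n = 20): rate, 95% CI | Group of 10: rate, 95% CI |
|---|---|---|
| 0 | 0.0% (0.0–16.8) | 0.0% (0.0–30.8) |
| 1 | 5.0% (0.1–24.9) | 10.0% (0.3–44.5) |
| 2 | 10.0% (1.2–31.7) | 20.0% (2.5–55.6) |
| 3 | 15.0% (3.2–37.9) | 30.0% (6.7–65.2) |
| 4 | 20.0% (5.7–43.7) | 40.0% (12.2–73.8) |

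The groups may not be exactly 10. With no events, the same formula gives 1 − 0.025^(1/9) = 33.6% for a group of 9 and 1 − 0.025^(1/11) = 28.5% for a group of 11.

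**Step 3: size of the difference.** At equal event counts the upper limits differ by a factor of 30.8 / 16.8 = 1.83 (0 events), 44.5 / 24.9 = 1.79 (1 event) and 55.6 / 31.7 = 1.75 (2 events). At equal observed rates the interval widths differ less. At 10% they are 44.2 and 30.5 points (ratio 1.45); at 20% they are 53.1 and 38.0 points (ratio 1.40).

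**Step 4: check the power figure.** The rule is to find the smallest r with P(X ≥ r) ≤ 0.025 at a true rate of 83%; power is then P(X ≥ r) at 95%.

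- n = 20: 20 of 20 has probability 0.83^20 = 0.0241, which passes. 19 or more has probability 0.0241 + 20 × 0.17 × 0.83^19 = 0.0241 + 0.0986 = 0.1227, which does not. So r = 20 and power = 0.95^20 = 35.8%. The plan's figure reproduces.
- n = 19: 0.83^19 = 0.0290 exceeds 0.025, and 19 of 19 gives a lower limit of 0.025^(1/19) = 82.4%. No result can meet the target.
- n = 21: power is 0.95^21 = 34.1%; at n = 22 it is 32.4%, falling to 21.5% at n = 30. At n = 31 one non-response is tolerated and power is 53.7%.

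**The case against.** The best defence of the table is that misreading is unlikely. Its first row shows a sample size of 20, the worked example repeats it, and the 1:1 split is stated in several places. The trial's own results will carry exact intervals on the real denominators (Protocol 8.5; SAP Appendix 5), so nobody has to interpret a dose group from the planning table. Sample size was set on practical grounds, the primary endpoint is safety, and no planned analysis tests against 83%. All of that limits the consequences. It does not make the caption right. Nor does reading group as cohort help, because both documents use treatment group for the dose arms and cohort for the populations.

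A reader might go further and infer that the power claim is also wrong, since 19 participants cannot meet the target and 21 give slightly under 35%. The documents do not support that. The sentence is conditional on a total of 20, and at 20 it is correct.

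A reader might also infer that unreplaced dropouts would bring the denominator to 19. They would not. Full Analysis Set membership depends on the complete long-acting regimen given on Day 1 (Protocol 8.3.1.2 and 5.3; SAP 3.1.2), and the snapshot algorithm keeps later dropouts in the denominator (SAP 6.1.2). Only under-enrolment, incomplete Day 1 dosing, or the chronic hepatitis B exclusion that SAP 6.3 declares can lower it.

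**Conclusion.** The caption is wrong as written in both documents. The limits describe the Primary Cohort total only. For a group of 10, the upper limit with no failures is 30.8% instead of 16.8%, and with one failure 44.5% instead of 24.9%. These figures assume 10 per group; modest imbalance does not alter the conclusion.

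It would be too strong to say that the table overstates group precision almost twofold in general. That describes upper limits at equal event counts; at equal observed rates of 10% or 20% the ratio of widths is 1.40 to 1.45.

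The power figure stands. What the plan leaves unsaid is that at 20 participants only a result of 20 out of 20 succeeds. It would also be too strong to say the stated power exists only at exactly 20: it is below 35% from 21 to 30 and exceeds it again at 31, outside the planned size. The matter concerns how precision is described. It does not touch the primary safety endpoint or any planned analysis.

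**What to change.** In Protocol Table 8-1 and SAP Table 1-1, change the end of the caption to *in Total (n = 20)* and add a block for a group of 10: 0 events 0.0% (0.0–30.8); 1 event 10.0% (0.3–44.5); 2 events 20.0% (2.5–55.6); 3 events 30.0% (6.7–65.2); 4 events 40.0% (12.2–73.8).

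Optionally, add after the power sentence: *With 20 participants in the Full Analysis Set the target is met only if all 20 respond (power 35.8%). It cannot be met with 19 or fewer, which could arise from under-enrolment, incomplete Day 1 dosing or the hepatitis B exclusion but not from dropout after dosing. Power is 34.1% with 21 and stays below 35% up to 30.*

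The cost is wording in two tables and, if adopted, one note. No design, data or analysis change is needed. The downside is that the stated per-group precision becomes less favourable. If the SAP is already final, its introduction provides for recording such changes in the clinical study report.

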9. RESPONSIBILITIES

9.1. Investigator Responsibilities

9.1.1. Good Clinical Practice

The investigator will ensure that this study is conducted in accordance with International Council for Harmonisation (of Technical Requirements for Pharmaceuticals for Human Use) (ICH) E6(R2) addendum to its guideline for GCP and applicable laws and regulations.

9.1.2. Financial Disclosure

The investigator and subinvestigators will provide prompt and accurate documentation of their financial interest or arrangements with Gilead, or proprietary interests in the study drug during the course of a clinical study. This documentation must be provided prior to the investigator's (and any subinvestigator's) participation in the study. The investigator and subinvestigator agree to notify Gilead of any change in reportable interests during the study and for 1 year following completion of the study. Study completion is defined as the date when the last participant completes the protocol-defined activities.

9.1.3. Institutional Review Board/Independent Ethics Committee Review and Approval

The investigator (or Gilead as appropriate according to local regulations) will submit this protocol, ICF, and any accompanying material to be provided to the participant (such as advertisements, participant information sheets, or descriptions of the study used to obtain informed consent) to an IRB/IEC. The investigator will not begin any study participant activities until approval from the IRB/IEC has been documented and provided as a letter to the investigator.

Before implementation, the investigator will submit to and receive documented approval from the IRB/IEC any modifications made to the protocol or any accompanying material to be provided to the participant after initial IRB/IEC approval, with the exception of those necessary to reduce immediate risk to study participants.

9.1.4. Informed Consent

The investigator is responsible for obtaining written informed consent from each individual participating in this study after adequate explanation of the aims, methods, objectives, and potential hazards of the study before undertaking any study-related procedures. The investigator must use the most current IRB- or IEC-approved ICF for documenting written informed consent. Each ICF (or assent as applicable) will be appropriately signed and dated by the participant or the participant's legally authorized representative, and the person conducting the consent discussion, and also by an impartial witness if required by IRB or IEC or local requirements.

The ICF will inform participants about genomic testing and/or planned sample retention. In addition to the study-specific ICF to be signed by each participant participating in the study, participants will be required to document agreement to provide additional samples or to allow the use of the remainder of their already collected specimens for optional future research, in accordance with applicable regulations. In addition to the study-specific ICF to be signed by each participant participating in the study, participants will be required to document agreement to provide additional samples for optional genomic research. The results of the tests done on the samples will not be given to the participant or the investigator.

9.1.5. Confidentiality

The investigator must ensure that participants' anonymity will be strictly maintained and that their identities are protected from unauthorized parties. Only an identification code and any other unique identifier(s) as allowed by local law (such as year of birth) will be recorded on any form or biological sample submitted to Gilead or the laboratory. Laboratory specimens must be labeled in such a way as to protect participant identity while allowing the results to be recorded to the proper participant. Refer to specific laboratory instructions. NOTE: The investigator must keep a screening log with details for all participants screened and enrolled in the study, in accordance with the site procedures and regulations. Participant data will be processed in accordance with all applicable regulations.

The investigator agrees that all information received from Gilead, including but not limited to the IB, this protocol, case report forms (CRFs)/eCRFs, the study drug information, and any other study information, remain the sole and exclusive property of Gilead during the conduct of the study and thereafter. This information is not to be disclosed to any third party (except employees or agents directly involved in the conduct of the study or as required by law) without prior written consent from Gilead. The investigator further agrees to take all reasonable precautions to prevent the disclosure by any employee or agent of the study site to any third party or otherwise into the public domain.

9.1.6. Study Files and Retention of Records

The investigator must maintain adequate and accurate records to enable the conduct of the study to be fully documented and the study data to be subsequently verified. These documents should be classified into at least the following 2 categories: (1) investigator's study file, and (2) participant clinical source documents.

The investigator's study file will contain the protocol/amendments, paper or electronic completed participant CRFs, and governmental approval with correspondence, the ICF(s), drug records, staff curriculum vitae and authorization forms, and other appropriate documents and correspondence.

The required source data should include sequential notes containing at least the following information for each participant:

- Participant identification
- Documentation that participant meets eligibility criteria, ie, medical history, physical examination, and confirmation of diagnosis (to support inclusion and exclusion criteria)
- Documentation of the reason(s) a consented participant is not enrolled
- Participation in study (including study number)
- Study discussed and date of informed consent
- Dates of all visits
- Documentation that protocol-specific procedures were performed
- Results of efficacy parameters, as required by the protocol
- Start and end date (including dose regimen) of study drug, including dates of dispensing and return
- Record of all AEs and other safety parameters (start and end date, and including causality and severity), and documentation that adequate medical care has been provided for any AE
- Concomitant medication (including start and end date, dose if relevant; dose changes)
- Date of study completion and reason for early discontinuation, if it occurs

All clinical study documents must be retained by the investigator for at least 2 years or according to local laws, whichever is longer, after the last approval of a marketing application in an ICH region (ie, US, Europe, or Japan) and until there are no pending or planned marketing applications in an ICH region; or, if no application is filed or if the application is not approved for such indication, for 2 years after the investigation is discontinued and regulatory authorities have been notified. Investigators may be required to retain documents longer if specified by regulatory requirements, by local regulations, or by an agreement with Gilead. The investigator must notify Gilead before destroying any clinical study records.

Should the investigator wish to assign the study records to another party or move them to another location, Gilead must be notified in advance.

If the investigator cannot provide for this archiving requirement at the study site for any or all of the documents, special arrangements must be made between the investigator and Gilead to store these records securely away from the site so that they can be returned sealed to the investigator in case of an inspection. When source documents are required for the continued care of the participant, appropriate copies should be made for storage away from the site.

